9.2 Procedures for the immediate notification of serious adverse events

Immediate notification of serious adverse events (expected or unexpected) by the investigator:

The Principal Investigator must report **immediately** to United BioSource Corporation Safety Team (CRO) all **serious adverse events (SAEs)** regardless of the study drug causality. The notification deadline (whether expected or unexpected) will be 24h from the moment the investigator first receives news of the event..

The initial submission of the SAE (whether expected or unexpected) must be done in less than 24h by email to United BioSource Corporation Safety Team (Contact email: [contact], [contact]).

Moreover, this information must be subsequently completed within a maximum of 3 days using the Serious Adverse Event Notification form. The form will be preferably sent via email or by fax to the above mentioned numbers.

In case of SAE (expected or unexpected), the investigator should provide to United BioSource Corporation Safety Team all the information related to the event (additional laboratory tests, discharge report, etc).

In case of death, the investigator should provide to United BioSource Corporation Safety Team and to the Ethics Committee/Institutional Review Board involved, all the additional information requested.

Serious and unexpected adverse events potentially related to the study drug will be promptly reported to the Ethics Committee/Institutional Review Board involved and to the Health Authorities in accordance with the applicable legislation. All adverse events will be reported tabulated in the final clinical trial report.

10. STATISTICAL METHODS

10.1.1 Analytical Populations

All subjects included in the study and subjected to at least one plasma exchange session (i.e., randomized and treated) during the intensive treatment phase (the six first weeks of treatment) will form part of the efficacy population.

Control group subjects will also be included (without the plasma exchange) if they attended at least 1 of the 6 intensive treatment phase visits.

A second efficacy analysis will also be carried out (per protocol analysis) with the patients who complete the treatment without major breaches in the study protocol.

10.1.2 Missing Data

Subjects with missing values for a given efficacy value at baseline or at the time point analyzed will be treated as missing rather than using imputed values. More details regarding handling of missing data will be provided in the statistical analysis plan (SAP).

10.1.3 Demographic and Baseline Characteristics

The demographic and baseline characteristics of the study patients will be presented in table form by treatment group and center. The results will also be expressed in total.

All continuous variables will be reported using standard statistical measures, i.e. number of observations, mean, standard deviation, minimum and maximum, median, and first and third quartiles.

All categorical variables will be summarized by frequency tables.

Equality of the baseline characteristics between the treatment groups will be assessed by descriptive methods.

10.2 Assessment of Efficacy

10.2.1 General

In general, the statistical tests will be performed with a 5% significance level and will be two-sided. In addition to the tests, two-sided 95% confidence intervals (95% CI) will be reported.

Specifically, the null hypothesis for all inferential analyses, including the primary endpoint, is that all three treatment groups are equal to placebo. Specific doses will be considered different from placebo if statistically significant following the Hochberg procedure described below. The study is considered positive if at least one dose group differs from placebo in the primary analysis. Subsequently, secondary endpoints are considered positive if at least one dose group differs from placebo.

More details will be provided in the statistical analysis plan (SAP).

10.2.2 Primary Endpoint

The co-primary endpoints, changes from baseline of the ADAS-Cog scores and change from baseline in the ADCS-ADL inventory, will be assessed with the principal analytical objective being to determine whether there are differences between each of the 3 treatment groups and the control group. In addition, a comparison between the 3 treatment groups will be performed.

Success of the study is determined by the change from baseline in the Total ADAS-Cog score at 14 months and the change from baseline in the ADCS-ADL inventory score. ADAS-Cog and ADCS-ADL scores at remaining time points are considered to be secondary to the scores at month 14. Missing

The mean change from baseline in both the ADAS-Cog and ADCS-ADL scores will be analyzed using analysis of covariance (ANCOVA) with adjustment for respective baseline as the covariate to compare the difference between each treatment group and the placebo group in the efficacy population.

If the data distribution assumptions are significantly violated, a non-parametric analysis will be used. If the test for either normality of error terms or equality of error variances fails at the significance level of 0.01, the rank ANCOVA procedure will be applied. The standardized ranks for both covariate and the response variable will be produced for each stratum. Then linear regression models will be performed on ranked data by stratum to generate the residuals. Finally the stratified mean score test using the value of the residuals as scores will compare the treatment groups using the Cochran-Mantel-Haenszel procedure.

Because the endpoints are co-primaries, both must be statistically significant for the study to provide evidence of efficacy. Therefore, no multiplicity adjustment is needed to adjust for the co-primary endpoints. However, to account for the three dose group comparisons to placebo and to maintain the overall significance level of 0.05, adjustment for α will be made for multiple dose groups according to the Hochberg procedure. The Hochberg procedure will be implemented as follows: For each endpoint the three dose group comparisons versus placebo will be ordered according to the p-value from the largest to the smallest. If the largest p-value is < 0.05 then all comparisons to placebo will be declared significant. Otherwise, if the second largest p-value is < 0.025 ($0.05/2$) then this dose and all doses with smaller p-values will be declared significant. Otherwise if the smallest p-value is < 0.0167 ($0.05/3$) then this dose will be declared significant. Otherwise, no dose is considered significantly different from placebo. This procedure has been demonstrated to control the overall Type I error at 0.05. Both co-primary endpoints must be significant at a given dose to provide evidence of efficacy for that dose.

A supportive analysis will be performed in per protocol analysis set for the primary efficacy endpoint applying the same respective methodologies, but without adjusting for Type I error.

10.2.3 Secondary Endpoints

All continuous secondary endpoints (Section 8.2) will be tested in a manner identical to the primary analysis, with the corresponding baseline used as the covariate.

10.3 Evaluation of Tolerability

The analysis of tolerability will be based on description of the safety variables according to their nature. In addition, a comparison of Adverse Drug Reactions between the treatment and the control groups will be performed.

The adverse reactions will be coded according to the adverse events classification of the World Health Organization (WHO) (MedRA current version), and will be described by a synonym (Lowest Level Term) and the affected organ / system, the intensity, causality and seriousness.

10.4 Intermediate Analysis and Stopping Rules

A descriptive analysis is planned once half of the subjects are undergoing low-volume plasma exchanges.

Serious adverse events related to full plasma exchanges (performed during the first six weeks), AEs leading to withdrawal of the study and additional safety measures if required will be monitored by the independent DMC on a regular basis. Special focus will be put on those SAEs considered as related to the therapeutic procedure or Investigational Product(s) by the Principal Investigator as defined in the protocol. Additional common side effects might also be analyzed if significantly higher proportions are found in any of the treatment arms.

Under the following circumstances the independent DMC will recommend to halt the trial partly (stopping a specific treatment arm) temporarily (until modifications to the protocol are completed) or wholly (abandon all study activities):

- If more than 30% of patients undergoing full plasma exchanges experience an SAE as defined by the protocol labeled “Definitively related to the therapeutic procedure” or “Probably related to the therapeutic procedure” or “Possibly related to the therapeutic procedure” and not attributable to the Investigational Products, as judged by the principal investigator.

- If more than 30% of patients undergoing full plasma exchanges experience an SAE as defined by the protocol labeled “Definitively related to the Investigational Product(s)” or “Probably related to the Investigational Product(s)” or “Possibly related to the Investigational Product(s)” and not attributable to the therapeutic procedure or technique of application, as judged by the principal investigator.

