5.1.3 Method of Application

Full plasma exchanges (Intensive treatment period)

Full plasma exchanges (FPE) can be carried out via peripheral access or centrally, according to the individual characteristics of the subject. In the latter case, and before the first replacement session, a double-lumen catheter must be placed in the subclavian or jugular vein. Implantation and maintenance will be carried out according to the standard procedures used in each center but it will be mandatory to perform a chest X-ray to confirm the correct placement of the catheter. Removed plasma volume will be replaced with the same volume of Albutein[®] 5% during the procedure.

The removed and replaced plasma volume will depend on patient's characteristics (sex, height, weight and hematocrit). It will be approximately 35-45 mL/kg, corresponding to a volume of 2500-3000 mL. This volume is calculated automatically by the device or manually by the operator depending on the device used.

For blinding the control group, adhesive gauze dressing will be placed on the subclavicular or jugular region, stitching a catheter of characteristics similar to the catheters used in the treatment group (see Appendix 9).

The central catheter has the advantage of increased convenience for the subject during the process, since it allows greater flows and thus shorter session times and obviates the need in each session to perform two peripheral venipunctures. The central line access also facilitates subject mobility during the procedure.

Each session is carried out at a rate of 60-100 mL/min., provided replacement is possible through a double-lumen catheter placed in the subclavian vein, with a continuous-flow cell separator. Each of these sessions will last approximately two to three hours. The control group will be subjected to simulated (sham) plasma exchanges during the same time as the subjects in the treatment group.

Each subject must remain in the facility throughout the procedure and then for as long as necessary to ensure a safe return home.

These details refer to the plasma exchange procedure performed through centrifugation (the most commonly used) although the procedure through filtration is also permitted.

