5.2.2.3 Allergic reaction

Allergic reactions are generally associated with the blood components and albumin, though they may also be due to ethylene oxide or other medication.

The signs and symptoms include:

- urticaria
- dyspnea
- wheezing
- hypotension
- tachycardia
- facial reddening
- palpebral edema

In case the patient suffers from an allergic reaction the site should follow their standard procedures to manage the situation. As a recommendation, mild allergic reactions could be controlled with antihistamines (diphenhydramine 25-50 mg i.v.). In case the reaction continues, or in the event of anaphylactic manifestations, it could be administered 0.3-0.5 mL of epinephrine 1:1000 s.c. This dose may be repeated after 10-15 minutes if no response is elicited. It is also possible to add methylprednisolone 100 mg i.v.

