5.2.2.4 Coagulation disorders

When the extracted plasma is replaced with albumin, coagulation disorders may develop due to dilution of the coagulation factors, mainly lowered blood fibrinogen, since its half-life is 72 hours. During daily plasma exchange sessions the fibrinogen concentration may drop to below 1 g/L, requiring the infusion of plasma or fibrinogen. When replacement is performed every 72 hours, such measures are not necessary.

Minor bleeding associated with severe thrombopenia has been observed (seen historically in approximately 2.2%).

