9.1.2 Imputability criteria

To analyze the possible relation cause-effect, it will be considered the temporal relationship between drug administration and the AE, possible alternative causes, evolution (complete remission, partial recovery, death and sequelae), persistence or not after drug discontinuation, reappearance with drug re-administration, or the previous knowledge of the event matching up with the known or expected response pattern of the study drug.

The following definitions will be used to establish cause-effect relationships:

Definitive: the adverse event occurs after a reasonable time sequence related to the study drug administration or study procedure, with a known response model, but cannot be explained by the patient clinical condition and other treatments provided, confirmed by improvement after interrupting or diminishing treatment dose, and with relapse after reintroducing treatment.

Probable: the adverse event occurs after a reasonable time sequence related to the study drug administration or study procedure, with a known response model, confirmed by improvement after interrupting treatment, and that cannot be explained by the patient clinical condition or other treatments provided.

Possible: the adverse event occurs after a reasonable time sequence related to the study drug administration or study procedure, with a known response model, but can be explained by the patient clinical condition and other treatments provided.

Unlikely: the adverse event occurs after a reasonable time sequence related to the study drug administration or study procedure, not following a known response model, and that cannot be explained by the patient clinical condition or other treatments provided.

Unrelated: Any other adverse event.

9.1.3 *Expected adverse events*

There are a series of **expected adverse events** attributable to the plasma exchange procedure, with others that are inherent to the replacement fluid used (human albumin). Lastly, other events are a consequence of patient disease or idiosyncrasy.

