The expected adverse events of plasma exchange are the following: hypocalcaemia (manifesting as paresthesias, headache, vision alterations, nausea, cramps and chest oppression), anaemia and coagulation disorders secondary to coagulation factor dilution (mainly hypofibrinogenemia, with possible minor bleeding associated to severe thrombopenia). Hypotension may occur (accompanied by paleness, perspiration, bradycardia, nausea, vomiting, syncope, sphincter relaxation and seizures); though the risk is minimal, since the infusion amount is equivalent to the extracted amount. Allergic reactions are also possible, with urticaria, dyspnea, wheezing, hypotension, tachycardia, facial reddening and palpebral edema. Other events may be of psychological origin or may be inherent to the process, such as for example pain after remaining immobile for several hours.

As indicated by the **Full Prescribing Information (Appendix 1)**, the Albutein[®] specific adverse events are mild reactions such as reddening, urticaria, fever and nausea. Such reactions are rare and normally subside when the perfusion rate is reduced or perfusion is suspended. Anaphylactic shock may be observed in isolated cases. In such situations, perfusion is to be suspended immediately with the provision of adequate treatment.

Albutein[®] is obtained from human plasma. The controls applied in the centers where the plasma is obtained, and in the fractionation plant, as well as the validated infectious agent inactivation/elimination procedures included in the production process, are all designed to minimize the risk of transmission of infectious disease. In any case, when dealing with blood products it is not possible to fully rule out possible transmission of infectious agents. This also refers to the possible transmission of unknown pathogens.

In a 1996 review of the adverse effects of plasma exchange in patients with Guillain-Barré syndrome involving albumin replacements, a decrease in immediate adverse effects from 12% in 1986 to 7% in 1992 was recorded. Allergic reactions and hypotension were the most frequent problems. The estimated mortality was 1-2 deaths per 10,000 sessions, or two deaths per 2000 patients.

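### Protocol 10.4: an SAE attributed to both the procedure and the product can count toward neither 30% halting criterion

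*Protocol*

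**What the plan says.** Protocol 10.4 lists two circumstances in which the DMC will recommend a partial, temporary or complete halt. Both use the same threshold, more than 30% of patients having full plasma exchange, and both accept the labels definitively, probably and possibly related.

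- Criterion 1 counts patients with an SAE related to the therapeutic procedure "and not attributable to the Investigational Products, as judged by the principal investigator".
- Criterion 2 counts patients with an SAE related to the investigational product(s) "and not attributable to the therapeutic procedure or technique of application, as judged by the principal investigator".

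There is no third or pooled criterion. SAP section 3, on interim analyses and unblinding, does not restate or change the rule.

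The causality scale in Protocol 9.1.2 is worded jointly for drug and procedure. Its Possible category, for example, covers an event in reasonable time sequence to "study drug administration or study procedure, with a known response model, but can be explained by the patient clinical condition and other treatments provided". Protocol 10.4 does not define attributable.

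SAP 7.2.2 plans a table of related adverse events by relationship, with product and procedure combined as a category of its own. The SAE form in Protocol Appendix 4 has one box for the relationship to study drug (box 13) and another for the relationship to other drugs or procedures (box 15).

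**The concern.** Each criterion removes events attributable to the other cause, so the two counts are mutually exclusive. An SAE attributed to both causes drops out of each.

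Such events can be expected, because the two exposures coincide. In every full exchange, according to Protocol 5.1.3, "Removed plasma volume will be replaced with the same volume of" albumin 5%. Allergic reactions are the clearest case. Protocol 9.1.3 lists them among the expected events of plasma exchange ("Allergic reactions are also possible, with urticaria, dyspnea, wheezing, hypotension, tachycardia"), while Protocol 5.2.2.3 states "Allergic reactions are generally associated with the blood components and albumin" and allows for anaphylactic manifestations.

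At stake is whether the only numeric halting triggers in the plan cover every SAE that the investigator relates to the intervention. Efficacy estimates, type I error and power are unaffected.

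**Working it through.** **Logic.** Let P be the patients with an SAE attributed to the procedure only, D those with one attributed to the product only, and B those whose related SAEs are all attributed to both. Criterion 1 counts P and criterion 2 counts D. B appears in neither.

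**How wording changes the size of B.**

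- If the exclusion qualifies all three labels, every dual SAE is lost. The clause closes both bullets in parallel form, which favours this reading.
- If it qualifies only the last label, the loss is limited to SAEs possibly related to both.
- If the reference to other treatments in the Protocol 9.1.2 scale includes the other study component, Definitive and Probable are largely ruled out for dual events, and the loss again falls on Possible.
- If attributable means one main cause per SAE, B is empty.

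**Trigger count.** The inputs are 364 planned subjects (Protocol 4.3) and 1:1:1:1 allocation to three treated arms and sham (Protocol 3.2).

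- Full-exchange patients: 364 × 3/4 = 273, assuming full enrolment and that every treated patient starts.
- Threshold: 0.30 × 273 = 81.9, so 82 patients fire a criterion and 81 do not. At earlier reviews the denominator, and so the count, is smaller.

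The protocol states no operating characteristic for this rule, so there is no figure of its own to reproduce.

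**Illustrative mix.** P = 60, D = 20, B = 40.

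| Count | As written | Dual SAEs counted in each |
|---|---|---|
| Any related SAE | 120/273 = 44.0% | 120/273 = 44.0% |
| Criterion 1 | 60/273 = 22.0%, no halt | (60 + 40)/273 = 36.6%, halt |
| Criterion 2 | 20/273 = 7.3%, no halt | (20 + 40)/273 = 22.0%, no halt |

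**Logical limits, not expected counts.** These are the most patients who could have a related SAE with no criterion firing:

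- as written: 81 + 81 + 111 dual-only = 273 of 273;
- with dual SAEs counted in each criterion: 81 + 81 = 162 of 273 (59.3%);
- with a single pooled criterion: 81 of 273 (29.7%).

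**Sensitivity to the unknown dual share.** Let d be the share of patients with a procedure-related SAE whose related SAEs are all dual. Criterion 1 then fires at 82/(1 − d) such patients, rounded up: 92 for d = 10%, 110 for d = 25%, 164 for d = 50%. With the exclusion removed it fires at 82. The values of d are assumed; the documents give none.

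**Background rate.** For plasma exchange with albumin replacement in another disease, Protocol 9.1.3 reports "a decrease in immediate adverse effects from 12% in 1986 to 7% in 1992 was recorded". Read as a share of patients, which the text does not specify, this gives 0.07 × 273 = 19.1 to 0.12 × 273 = 32.8 patients. That covers events of any severity and lies well below 82.

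**The case against.** The best reply is that the clauses sort events by main cause. Protocol 9.1.3 divides expected events into those of the procedure, those of the replacement fluid and those of the patient, and Protocol 5.2.2 divides them similarly. If the investigator must choose one cause, each SAE counts once and none is lost. This reading is possible, but neither document instructs the investigator to choose, and the SAP's combined category points the other way.

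The evidence that dual SAEs will be frequent is thin, and this part of the reply stands. Protocol 5.2.2.4 says "When the extracted plasma is replaced with albumin, coagulation disorders may develop due to dilution of the coagulation factors", which looks like a dual event, but Protocol 9.1.3 lists factor dilution under plasma exchange and keeps albumin's own reactions separate. It calls those reactions mild and rare, with anaphylactic shock in isolated cases. The SAP table covers all adverse events in both treatment periods, not only SAEs of the full-exchange phase. It therefore shows that dual attribution is foreseen, not that it is common.

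Oversight outside the two criteria also stands as mitigation. Protocol 10.4 directs the DMC's special focus to SAEs related to the procedure or the product, which takes in dual events. Protocol 12.4 gives it unblinded event rates by arm and the power to recommend early termination. A reader might infer that dual SAEs would escape the DMC, or that every treated patient could suffer a related SAE unnoticed. The documents do not support either: the 273-of-273 figure describes the two triggers alone, in an extreme configuration.

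**Conclusion.** The gap is real but minor. Unless attributable means a single forced main cause, Protocol 10.4 leaves SAEs attributed to both procedure and product out of both numeric criteria. On the narrowest reading short of that, it leaves out SAEs possibly related to both.

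Its practical size cannot be estimated, because the documents give no rate of dual attribution; the 44% mix, the limits and the values of d are illustrations only. The 82-patient trigger assumes full planned enrolment, but the logical point does not depend on it. The threshold is far above the quoted background, so the rule is a backstop that is unlikely to fire at background rates however dual events are counted. It should still not omit events that the investigator relates to both parts of the intervention.

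**What to change.** In Protocol 10.4, delete both exclusion clauses, or add a sentence that an SAE related to both the procedure and a product counts in each criterion. Keep the 30% threshold of full-exchange patients, the three causality labels and the two separate counts.

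Take the procedure relationship from the CRF, where SAP 7.2.2 says it is recorded, and not from box 15 of the SAE form, which pools procedures with other drugs. On the SAP's account no new data item is needed, although the CRF itself is not among the documents.

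Costs:

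- a short protocol amendment with IRB notification (Protocol section 11), and a matching change to any DMC document that repeats the rule;
- a trigger that is somewhat easier to reach, for example 82 instead of 92 patients with a procedure-related SAE if d were 10%;
- some loss of separation, because a dual event no longer tells the DMC whether the procedure or the product is at fault. Reporting the dual count alongside the two criteria would limit this.

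The change does not create a pooled cap: up to 162 of 273 patients could still have a single-cause SAE with neither criterion met. Whether to cap that total is a separate decision.
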